## Sensitivity analyses

The best-case scenario will consist in deleting patients without data at M6 and M12 (if M12 is available then M12 will be imputed at M6).

- The worst-case scenario will consist in imputing a total loss of hearing (score = 0%)
- Tipping point analysis approach will be applied to assess the rules which overturn the conclusion. The steps going from the best scenario to the worst one (all missing scores are 0) and including rules of the primary analysis.

## 4. Analysis population

### 4.1. Full Analysis Set (FAS)

The Full Analysis Set will include all subjects implanted with the device, regardless whether any post-operative data are available.

The primary analysis will be performed on a subgroup of this set. This subgroup will be composed of English-speaking patients to avoid the probable effect of language on the response.

### 4.2. Per Protocol Set (PPS)

The Per Protocol Set will include all patients of the FAS and who will complete the clinical trial according to the protocol.

It consists of subjects who will satisfy the following criteria:

- Completion of the pivotal study
- Protocol compliance during the pivotal study
- No violation of any eligibility criteria that could influence the primary efficacy endpoint
- No violation of the protocol or deviation from the protocol which could influence the outcome of efficacy endpoints

The English-speaking subgroup in the PPS will be used in a sensitivity analysis of the primary analysis.

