**Visit 8 (end of study, Month +12 post-activation)**

- Audiometric evaluations: HINT-Q, HINT-N
- Audiometric evaluations in routine care shall be recorded, if available
- Objective measures: electrode impedances and ECAP shall be recorded
- Review of returned Subject's diary
- Complications/adverse effects shall be recorded
- Concomitant medication(s) shall be recorded

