##### b) Per-Protocol Set (PPS)

This set of patients is composed of participants who complete the clinical trial according to the protocol.

It consists of subjects who satisfy the following criteria:

- Complete the pivotal study
- Protocol compliance during the pivotal study (complete post-implantation visits)
- No violation of any eligibility criteria that could influence the primary efficacy endpoint
- No violation of the protocol or deviation from the protocol which could influence the outcome of efficacy endpoints.

The type of protocol violation and protocol deviations that are considered to influence the outcome of the safety endpoints will be defined in the statistical analysis plan.

The English speaking subgroup in the PPS will be used in a sensitivity analysis of the primary analysis.

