### 5.1. Follow-up of the study

- Number of patients in each analysis data sets according to the decisions made during the Data Review meeting to determine major/minor protocol deviations (refer to table 1).
- Number of patients present at each visit and listing of patients not present at one visit (refer to table 1).
- Time between visits (refer to table 6):
  - Date of surgery (V3) – Date of inclusion (V2) (days)
  - Date of activation (V5) – Date of surgery (V3) (days)
  - Date of follow-up visits (V4, V6, V7 and V8) – Date of surgery (months)
  - Date of unscheduled visit – Date of surgery (V3) (months)
  - Date of end of visit (V8) – Date of surgery (V3) (months)
- Discontinuation: Yes / No (refer to table 2)  
Patient will be considered as withdrawn:
  - If the question “did the patient complete the study” is answer “NO”  
OR
  - if the end of study visit is not performed
  - If YES, reasons of discontinuation: Screen failure / Adverse event / Death / Patient request / Investigator decision / Loss to follow-up / Protocol violation / Study terminated by the sponsor / Other
- The patient disposition will be provided as described in the figure 1. It will include the following information:
  - Number of subjects screened; included
  - Withdrawals and reasons
  - Protocol violations/deviations and exclusions from each data sets
  - Number of patients in each analysis data sets

[figure not shown]

FIGURE 1 : PATIENT DISPOSITION DIAGRAM

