## 5.6. Primary end point

### 5.6.1. HINT in Quiet at Month 6

Change from baseline to month 6 (refer to table 8).

Calculation = HINT-Q at Month 6 - HINT-Q at Inclusion visit

The primary efficacy endpoint of the Neuro CIS is assessed with the HINT score in quiet, on the ipsilateral ear.

The mean HINT scores in quiet will be used as the primary outcome measures for assessing the primary benefit.

The primary analysis will be performed on a subgroup of the FAS which consists of all English-speaking patients (Exclusion of Danish and French-Canadian speaking patients). The analysis will be replicated in PPS.

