## 6. Statistical analysis

### 6.1. Analysis of efficacy endpoint

The primary analysis of the primary efficacy endpoint will be performed on a subgroup of the FAS which consists of all English-speaking subjects.

Additional analysis with a replicate PPS will be performed on this subset of English-speaking patients.

The primary test is a one sample T-test performed on the change from baseline to 6 months after activation of the device. The value of the mean improvement under the null hypothesis is zero. The type I error ( $\alpha$ ) is set to 0.025 (one-sided).

The one sample Wilcoxon rank test will be applied in a sensitivity analysis. In case the normality assumption is strongly violated or in the presence of several outliers, the result of this sensitivity analysis will have a particular importance.

To further describe the benefit of the Neuro CIS in the studied population, the number of patients (as well as rate among the total population) showing a benefit of at least 20 percentage points in HINT-Q score after 6 months of device use when compared to baseline will be computed (table 8 with the related figure and table 16.6).

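### The per-protocol set used to check the month-6 endpoint requires attendance to month 12, so patients with a valid month-6 score can be dropped for later events, shifting the mean in an unknown direction

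*SAP*

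**What the plan says.** SAP 4.2 defines the set as follows: "The Per Protocol Set will include all patients of the FAS and who will complete the clinical trial according to the protocol". The first listed criterion is "Completion of the pivotal study". Protocol 3.6.2.1 b) has the same criterion and adds "Protocol compliance during the pivotal study (complete post-implantation visits"; the SAP's version of that second bullet leaves out the words in parentheses.

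The end of the study is fixed by the visit schedule in protocol 3.5.7: "Visit 8 (end of study, Month +12 post-activation". SAP 5.1 counts a patient as withdrawn if the completion question is answered no, or "if the end of study visit is not performed".

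The primary endpoint is complete earlier. SAP 5.6.1 gives "Calculation = HINT-Q at Month 6 - HINT-Q at Inclusion visit", and SAP 6.1 states "The primary test is a one sample T-test performed on the change from baseline to 6 months after activation of the device". The per-protocol set bears on this endpoint because SAP 4.2 says "The English-speaking subgroup in the PPS will be used in a sensitivity analysis of the primary analysis". The primary analysis itself uses English speakers in the full analysis set (FAS), which takes in every implanted subject whether or not follow-up data exist (SAP 4.1). SAP version 3.0 extended the per-protocol replication to all analyses done on the FAS.

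Neither document makes an exception for a patient who has a month-6 score but no visit 8.

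**The concern.** Membership of the month-6 sensitivity set depends on what happens between month 6 and month 12. A patient who met every requirement through visit 7 and then left has an observed, on-protocol endpoint that the check discards. If leavers differ from stayers in their month-6 result, the per-protocol column of Table 8 estimates the change in patients who went on to finish the year. That is not the change in patients who followed the protocol up to the endpoint. The difference between the FAS and per-protocol estimates then mixes protocol adherence with later attendance.

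The other planned sensitivity analyses do not cover this. The best-case, worst-case and tipping-point scenarios (protocol 3.6.3.2, SAP section 3) act on missing scores, and these patients' month-6 scores are not missing.

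The same filter reaches the month-3 and month-6 secondary results for HINT-Q and HINT-N, because SAP 6.3.1 to 6.3.4 repeat them in the per-protocol set.

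**Working it through.** **1. The plan's own figure.** Protocol 3.6.1.4 and SAP 1.3 give 7 patients for 95% power, with mean change 50, SD 25 and one-sided alpha 0.025. For a one-sample t-test, power comes from the noncentral t with n - 1 degrees of freedom and noncentrality (50/25) × √n. This gives 90.9% at n = 5, 97.1% at n = 6 and 99.1% at n = 7. The exact minimum is 6, so the stated 7 is adequate and slightly generous. Efficacy power is not the issue.

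**2. Who is removed.** Take a patient with valid HINT-Q at visits 2 and 7 and no visit 8.
- FAS: included, with the observed month-6 change.
- Per-protocol set: excluded, because the study ends at visit 8 and the patient has not completed it.

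Now take a patient who missed visit 7 but attended visit 8. Under the protocol's wording this patient is out. Under the SAP's shorter wording the patient could stay in, with the month-12 score standing in for month 6 (missing-data Rule 1), unless the data review counts the missed visit as a relevant deviation. For a month-6 check, that is the wrong way round.

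**3. Size of the shift.** Inputs are 39 English speakers (the planned minimum in both documents) and a mean change of 50 in those retained (the planning value). Assume that all 39 have a month-6 score and that only this criterion separates the two sets. Let k be the number removed and m their mean change at month 6.

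FAS mean = [(39 - k) × 50 + k × m] / 39

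Shift = per-protocol mean - FAS mean = k × (50 - m) / 39

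The documents give neither k nor m, so both are assumed over a range.

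| k removed | m = 0 | m = 20 | m = 50 | m = 70 |
|---|---|---|---|---|
| 1 | +1.28 | +0.77 | 0 | -0.51 |
| 2 | +2.56 | +1.54 | 0 | -1.03 |
| 3 | +3.85 | +2.31 | 0 | -1.54 |
| 4 | +5.13 | +3.08 | 0 | -2.05 |
| 5 | +6.41 | +3.85 | 0 | -2.56 |

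The range is -2.6 to +6.4 points, and its sign is set entirely by m. With membership fixed at visit 7, the shift from later non-completion is 0.

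**4. Effect on the test.** Take k = 5 with all five at zero change, and SD 25 among the 34 retained.
- FAS: mean 34 × 50 / 39 = 43.6, SD 28.8, t = 43.6 / (28.8/√39) ≈ 9.5.
- Per-protocol set: t = 50 / (25/√34) ≈ 11.7.

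The critical value is about 2.0, so both tests reject by a wide margin.

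**The case against.** The strongest case against acting is that nothing decisive rests on this set. The primary analysis keeps every observed month-6 score, protocol 3.6.2.4 confines labelling claims to the primary analysis, and the test has a very large margin. Table 8 shows the FAS and per-protocol results side by side, and Table 2 lists reasons for discontinuation, so a gap would be visible. A single completer set is also a common convention. All of that stands, and it limits the point to how the per-protocol estimate is read. It does not remove the point: a visible gap still could not be attributed to adherence rather than to later attendance.

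Three stronger readings are tempting but are not supported.
- **That the check leans towards success.** Protocol 3.5.4 wants withdrawals examined for a possible contribution from device failure, so low month-6 scores among leavers are plausible. Neither document says how such patients scored, and a good scorer who moves away would pull the per-protocol mean down.
- **That every explanted patient or non-user is removed.** Under the completion criterion, a patient who still attends visit 8 has completed the study. Such a patient might be excluded under the compliance or deviation criteria, but that is a different rule.
- **That the 10% in protocol 3.5.4 is a planned loss after month 6.** It is a replacement threshold for the whole sample of 55 over the whole study. Four of 39 lost after month 6 is an illustration only.

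**Conclusion.** The point holds as a flaw in how the sensitivity set is defined. A set meant to check a month-6 endpoint is conditioned on reaching month 12, and no exception is written. The consequence is a possible shift in the per-protocol mean change of about -2.6 to +6.4 points. That range assumes 39 English speakers, a retained mean of 50, 1 to 5 removals and a mean change among those removed between 70 and 0. The definition follows directly from the text. The number of removals and their scores are assumptions, and the direction is open. The primary FAS estimate and its significance do not change, so this is a cheap improvement and not a threat to the trial's conclusion.

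**What to change.** Define per-protocol membership by endpoint.
- **Month-6 analyses:** eligibility met, no relevant deviation, and valid HINT at visits 2 and 7, all judged through visit 7 only. This also settles the case of a completer without a month-6 test.
- **Month-12 and sustainability comparisons:** additionally require visit 8.
- **Joint models of months 3, 6 and 12 (SAP 6.3.1 and 6.3.3, and their HINT-N counterparts):** state that they use the visit-7 set with all observed visits. Otherwise their per-protocol population is left undefined.

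Make the same change in protocol 3.6.2.1 b), SAP 4.2 and the per-protocol rows of Table 1.

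The cost is two membership flags in place of one, with slightly different counts. No new data, visits or patients are needed. Timing needs care: SAP version 3.0 is dated 27/01/2020, after the planned completion in December 2019, and the study is open label. If the change is adopted late, record the reason and show the present completer set alongside the new one.

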### 4.3. Safety Analysis Set (SAS)

The Safety Analysis Set will include all patients for whom the surgery of implantation started.

## 5. Data analysis

All statistical analysis will be generated using SAS version 9.4.

### 5.1. Follow-up of the study

- Number of patients in each analysis data sets according to the decisions made during the Data Review meeting to determine major/minor protocol deviations (refer to table 1).
- Number of patients present at each visit and listing of patients not present at one visit (refer to table 1).
- Time between visits (refer to table 6):
  - Date of surgery (V3) – Date of inclusion (V2) (days)
  - Date of activation (V5) – Date of surgery (V3) (days)
  - Date of follow-up visits (V4, V6, V7 and V8) – Date of surgery (months)
  - Date of unscheduled visit – Date of surgery (V3) (months)
  - Date of end of visit (V8) – Date of surgery (V3) (months)
- Discontinuation: Yes / No (refer to table 2)  
Patient will be considered as withdrawn:
  - If the question “did the patient complete the study” is answer “NO”  
OR
  - if the end of study visit is not performed
  - If YES, reasons of discontinuation: Screen failure / Adverse event / Death / Patient request / Investigator decision / Loss to follow-up / Protocol violation / Study terminated by the sponsor / Other
- The patient disposition will be provided as described in the figure 1. It will include the following information:
  - Number of subjects screened; included
  - Withdrawals and reasons
  - Protocol violations/deviations and exclusions from each data sets
  - Number of patients in each analysis data sets

[figure not shown]

FIGURE 1 : PATIENT DISPOSITION DIAGRAM

## 5.2. Baseline characteristics

(refer to table 3)

- Age: Calculation (years) = (date of visit V2 – date of birth)/365.25  
Classes (years): [18 – 35[; [35 – 50[; [50 – 70[;  $\geq 70$
- Gender: Male / Female
- BMI: Calculation ( $\text{kg}/\text{m}^2$ ) = weight (kg) / height (m)  
Classes ( $\text{kg}/\text{m}^2$ ): [18 – 25[; [25 – 30[; [30 – 35[;  $\geq 35$
- Language speaking: English / French / Danish

## 5.3. Medical history

(refer to table 4)

- Allergies: Yes / No  
If Yes, cause and type of reaction (will be presented through a listing classified by allergy and patient)
- Significant medical history: Yes / No  
Calculation: YES is defined as at least, one disease/syndrome ticked Past
- Significant concomitant disease: Yes / No  
Calculation: YES is defined as at least, one disease/syndrome ticked Present
- Concomitant medication: Yes / No  
Calculation: YES is defined as patient with at least one concomitant treatment  
Frequency of treatment classified according to the ATC classes

## 5.4. Hearing history

(refer to table 5)

- Etiology:  
Frequency of primary cause by ear (right / left): Aging / Auto immune / Genetics / Noise exposure / Otosclerosis / Meniere's disease / Acoustic neuroma / Meningitis / Mondini / Head trauma /Viral / Ototoxic drugs / Unknown / Other cause
- Hearing history:
  - Duration of hearing loss for each ear (right / left) (years):

Calculation: Age of first used hearing aid – Age at onset of hearing loss, or  
 Calculation: Age at cochlear implantation - Age of onset of hearing loss

- Duration of hearing sensorial hearing loss for each ear (right / left) (years)  
 Calculation: Age at cochlear implantation – Age at onset of severe to profound hearing loss
- Vertigo: Yes / No
- Tinnitus: Yes / No
- Diagnostic imaging:
  - CT imaging: Yes / No  
 If Yes, results: bony labyrinth anomaly, cochlear malformation, ossification
  - MRI: Yes / No  
 If Yes, results: auditory nerve lesions, cochlear malformation, ossification/fibrosis, central lesions of the auditory pathway
- Audiological assessment:
  - Pure tone audiometry:  
 Duration = Date of visit 2 – Date of audiometry assessment  
 For each ear (right / left), values of dB for each tested frequency: 250 Hz / 500 Hz / 1 kHz / 2 kHz / 4 kHz / 8 kHz
  - Performance of Tympanometry: Yes / No  
 if YES, results by ear (right / left):
  - Speech perception test: percentage of correct words for HINT-Q and HINT-N tests
  - Performance-of Speech audiometry routine test: Yes / No  
 if YES, results by patient will be presented through a listing

## 5.5. Surgery

(refer to table 7)

- Ear implanted: Right / Left
- Cochlear implant type: Neuro Zti CLA / Neuro Zti EVO
- Full electrode array insertion : yes/no
- Number of electrodes out of cochlea,
- Time of surgery (min)

- Objective measures: Yes / No
  - If YES, performance of impedance and ECAP testings: Done / Not done / Meet an issue
  - If Impedance DONE: value (kilo ohms) for the 20 channels
  - If ECAP DONE: Download the results into the eCRF

## 5.6. Primary end point

### 5.6.1. HINT in Quiet at Month 6

Change from baseline to month 6 (refer to table 8).

Calculation = HINT-Q at Month 6 - HINT-Q at Inclusion visit

The primary efficacy endpoint of the Neuro CIS is assessed with the HINT score in quiet, on the ipsilateral ear.

The mean HINT scores in quiet will be used as the primary outcome measures for assessing the primary benefit.

The primary analysis will be performed on a subgroup of the FAS which consists of all English-speaking patients (Exclusion of Danish and French-Canadian speaking patients). The analysis will be replicated in PPS.

### 5.6.2. Major complication incidence rate

The occurrence of major complications within the first year of follow-up will be the co-primary endpoint for assessing the primary risk of device implantation.

Safety data shall be collected through the duration of the study and reflect the type and duration of any adverse event(s) and classified as major or minor complications. An AE is any adverse change from the subject's baseline condition, symptoms or disease which is considered to be clinically relevant by the investigator that occurs whether or not it is considered to be related to the medical device. A complication is any adverse change symptoms or disease related to the surgery or the medical device. Complications will be classified as major if they require surgical intervention or not recovered spontaneously and minor if they resolve spontaneously or with non-invasive medical treatment categories (according to Cohen and Hoffman criteria).

Three incidence rates will be calculated and provided (refer to tables 9 and 16.1):

- Major complications rate which will be considered as a co-primary estimate of device side-effects
- Minor complications rate which will be considered as a secondary evaluation of side-effects
- Incidence rate of any complications

## 5.7. Secondary efficacy endpoints

### 5.7.1. Time course of the change of HINT-Q

Calculation of change from baseline =

Percent of correct words of HINT-QMonth 3/6/12 – Percent of correct words of HINT-QInclusion visit  
(Refer to tables 8,10 and 11)

### 5.7.2. Homogeneity of HINT-Q results across languages

Calculation of change HINT-QMonth 3/6/12 =

Percent of correct words of HINT-QMonth 3/6/12 – Percent of correct words of HINT-QInclusion visit  
(refer to tables 12)

### 5.7.3. Sustainability of the effect at 12 months

Calculation of change HINT-Q at Month 6/12 = Percent of correct words of HINT-Q at Month 6/12 – Percent of correct words of HINT-Q at 3/6 months

Calculation of change HINT-Q at Month 12-3 = Percent of correct words of HINT-Q at Month 12 – Percent of correct words of HINT-Q at 3 months in case of the change between Month 12 and Month 6 is not significant.

Applicable across language if no effect on language (refer table 12), otherwise applicable only on English-speaking subjects (11.1).

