## **3.6 Study Outcome Evaluations**

### **3.6.1 Study Endpoints**

#### **3.6.1.1 Primary Endpoints**

Previous studies analyzed their samples based on fixed time intervals after implantation, usually 1, 3 and 6 months, then annually thereafter. After 6 months of CI experience outcomes appear to be stable with the majority of users reaching a performance plateau. Massa et al. [5] observed a performance plateau at a median of 4.7 months post-implantation. Similar results were reported by Bradley et al. [8] demonstrated a plateaued performance around 6 months in a sample of 55 patients. In Dillon et al. study [9] the adults tested with HINT in quiet at 70 dB experienced growth in speech perception within the first 6 months and remained stable thereafter. This plateau at 6

months is generally consistent with findings from others previous research with other speech discrimination tools, as Lenarz et al. study [7] using German language tests in a large cohort.

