**b) Sustainability of the effect at month 12**

HINT in quiet conditions performed at month 6 in English speakers will be compared to the result at month 12 to assess the sustainability of the effect over time. A one-sided ( $\alpha = 0.025$ ) t-test for paired samples will be used for that purpose.

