### **6.3.2. Sustainability of the effect at 12 months in FAS and PPS**

HINT-Q performed at Month 6 in the FAS and PPS sub-group of English speaking patients will be compared to the result at Month 3, and the result at month 12 will also be compared to those obtained at Month 3 and 6 to assess the sustainability of the effect over time.

A one-sided ( $\alpha = 0.025$ ) t-test for paired samples will be used. (refer to tables 11.1 and table 11.2).

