**Figure N (to be done with data in the SAR) : Forest plot of major complications incidence rate**

**Table 10: Assessment of secondary endpoints – Time course of the HINT-Q response – FAS and PPS English speaking patients' sub-group**

Source	Model parameter	df	Sum of squares	Mean Ssquare	F Value	Pr > F	R-Square
Model	Change HINT-Q						
Error	Patient Visit						
Corrected Total							

**Table 11.1 : Assessment of secondary endpoints – Sustainability of the effect of HINT-Q at Month 12 – FAS and PPS English speaking patients sub-group**

	English speaking patients (FAS) N=	English speaking patients (PPS) N=
HINT-Q at baseline – Percent of correct words	x.xx±x.x CI= [x.x;x.x] [xx ; xx] Med=x Missing=x	x.xx±x.x CI=[x.x;x.x] [xx ; xx] Med=x Missing=x
HINT-Q at Month 3 – Percent of correct words	x.xx±x.x CI= [x.x;x.x] [xx ; xx] Med=x Missing=x	x.xx±x.x CI=[x.x;x.x] [xx ; xx] Med=x Missing=x
HINT-Q at Month 6 – Percent of correct words	x.xx±x.x CI= [x.x;x.x] [xx ; xx] Med=x Missing=x	x.xx±x.x CI=[x.x;x.x] [xx ; xx] Med=x Missing=x
HINT-Q at Month 12 – Percent of correct words	x.xx±x.x CI= [x.x;x.x] [xx ; xx] Med=x Missing=x	x.xx±x.x CI=[x.x;x.x] [xx ; xx] Med=x Missing=x
Change at Month 3 (vs baseline) – Percent of correct words	x.xx±x.x CI= [x.x;x.x] [xx ; xx] Med=x Missing=x	x.xx±x.x CI=[x.x;x.x] [xx ; xx] Med=x Missing=x
P value	x.xxx	x.xxx
Change at Month 12 (vs baseline) – Percent of correct words	x.xx±x.x CI= [x.x;x.x] [xx ; xx] Med=x Missing=x	x.xx±x.x CI=[x.x;x.x] [xx ; xx] Med=x Missing=x

P value	x.XXX	x.XXX
Change from M3 to M6 – Percent of correct words	x.XX±x.X CI= [x.X;x.X] [xx ; xx] Med=x Missing=x	x.XX±x.X CI= [x.X;x.X] [xx ; xx] Med=x Missing=x
P value	x.XXX	x.XXX
Change from M3 to M12 – Percent of correct words	x.XX±x.X CI= [x.X;x.X] [xx ; xx] Med=x Missing=x	x.XX±x.X CI= [x.X;x.X] [xx ; xx] Med=x Missing=x-
P value	x.XXX	x.XXX
Change from M6 to M12 – Percent of correct words	x.XX±x.X CI= [x.X;x.X] [xx ; xx] Med=x Missing=x	x.XX±x.X CI= [x.X;x.X] [xx ; xx] Med=x Missing=x
P value	x.XXX	x.XXX

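### The SAP files month 12 versus month 3 under sustainability, conditionally in 5.7.3 and unconditionally in 6.3.2 and Table 11.1, whereas the protocol rests sustainability on month 6 versus month 12 alone

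*SAP*

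**What the plan says.** **Protocol.** Section 3.6.2.4 b states: "HINT in quiet conditions performed at month 6 in English speakers will be compared to the result at month 12 to assess the sustainability". Section 2.4.2 uses the same two visits for HINT-Q and again for HINT-N. Section 3.6.2.4 c also uses month 6 versus month 12 for sustainability in all languages combined. Month 3 appears in none of these definitions.

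**SAP 5.7.3.** Under the sustainability heading it lists the changes from month 3 to month 6 and from month 6 to month 12. It then adds month 12 minus month 3, to be calculated "in case of the change between Month 12 and Month 6 is not significant".

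**SAP 6.3.2.** Under the same heading, month 6 is set against month 3. The section then says: "the result at month 12 will also be compared to those obtained at Month 3 and 6 to assess the sustainability of the effect". There is no condition. The test is a paired t-test at one-sided 0.025, with no direction stated.

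**SAP Table 11.1.** The mock table, titled as sustainability, has rows for "Change from M3 to M12" and "Change from M6 to M12", each with a confidence interval and a p-value and neither conditional. Table 13 has the corresponding rows for HINT-N, to which SAP 5.7.4 extends the 5.7.3 calculations.

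**The concern.** There are two linked problems.

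First, the SAP gives two instructions for one analysis. If month 12 differs significantly from month 6, a programmer following 5.7.3 leaves out the month 3 to month 12 result. One following 6.3.2 and Table 11.1 prints it.

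Second, month 3 is the wrong reference for maintenance after month 6. Protocol 3.6.1.1 cites patients who "experienced growth in speech perception within the first 6 months and remained stable thereafter", and a plateau at a median of 4.7 months after implantation. The month 3 visit falls at about month 4 after surgery (protocol 3.5.5.4), so on the protocol's own evidence some patients may still be improving then. A gain from month 3 to month 12 may therefore reflect late learning.

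Sustainability is a named secondary objective, and neither document says which result would count as sustained. A significant gain printed under that heading invites the wrong answer, and 5.7.3 calls for it exactly when the comparison the protocol asks for is inconclusive.

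**Working it through.** **Plan figures.** The documents give no power, SD or margin for sustainability. The planned 7 patients relate to the primary test (50 points, SD 25, one-sided 0.025, 95% power). Exact t-test power is 97.0% at n = 6 and 99.1% at n = 7, so that figure is adequate, but it does not bear on this point.

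**Identity.** M12 − M3 = (M6 − M3) + (M12 − M6). With a rise of 10 and then a fall of 4, M12 − M3 = 10 − 4 = +6.

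**Inputs.**
- From the documents: n = 39 English-speaking patients (SAP 1.3), before any dropout, and paired t-tests. The condition is read as two-sided 5%, following SAP section 3, because 6.3.2 states no direction.
- Assumed: the rise, the fall, and the SD of a between-visit change. The only planning SD in the documents is 25, for change from baseline. Errors are taken as independent with equal variance at each visit.

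**Step 1: how large an observed fall passes as not significant.** The limit is t(0.975, 38 df) × SD/√39, with t = 2.024 and √39 = 6.245.
- SD 12: 2.024 × 12/6.245 = 3.9 points
- SD 15: 2.024 × 15/6.245 = 4.9 points
- SD 25: 2.024 × 25/6.245 = 8.1 points

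**Step 2: a true rise of 10 and fall of 4.** The noncentrality is (true change) × √39/SD.

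| SD | M12 − M6 (−4) | P(not significant) | M12 − M3 (+6) |
|---|---|---|---|
| 12 | −2.08 | 0.47 | 3.12 |
| 15 | −1.67 | 0.63 | 2.50 |
| 25 | −1.00 | 0.84 | 1.50 |

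**Step 3: both results together.** This is the probability that M6 to M12 is not significant and M3 to M12 shows a significant gain, from 40,000 simulated trials per row.

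| Rise, fall | SD | Probability |
|---|---|---|
| +10, −4 | 12 | 0.45 |
| +10, −4 | 15 | 0.50 |
| +10, −4 | 25 | 0.29 |
| +5, −4 | 12 to 15 | 0.05 to 0.06 |
| +10, −8 | 12 to 15 | 0.01 to 0.04 |

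The probability is high only when the rise clearly exceeds the fall and the fall is small enough to miss significance.

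**Step 4: what the condition does.** For +10 and −4, a significant M3 to M12 gain occurs in 86% (SD 12) or 68% (SD 15) of trials if the comparison is always made, against 45% and 50% when it is made only after a non-significant M6 to M12 result. A condition tested two-sided, or for decline, therefore removes some of the misleading gains. If the undirected one-sided test is read as a test for improvement, a fall almost never makes it significant, and the figures return to 86% and 68%.

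**The case against.** The strongest reply is that this is a matter of headings. Table 11.1 always prints the month 6 to month 12 change with its interval and p-value, and Table 13 does so for HINT-N. Table 11.1 also holds changes from baseline, so its title reads as a container and not as a conclusion attached to each row. Protocol 3.6.2.4 makes secondary analyses supportive and confines labelling claims to the primary analysis. A 4-point loss is small beside the 20 points called clinically pertinent and the 50 expected. SAP 6.3.1 already looks for differences between visits as time course.

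Most of this stands, and it rules out several stronger readings that a reader might infer:
- *That the SAP conceals a decline, or lets the month 3 comparison replace the month 6 one.* No rule does either.
- *That the month 3 comparison is made only after a non-significant result.* This is true of 5.7.3 but not of 6.3.2 or Table 11.1.
- *That month 12 minus month 3 is positive by design.* It is expected to be positive only if scores still rise after month 3 by more than they later fall. The cited plateau makes some rise plausible, but no document gives its size.
- *That about half of such trials would mislead.* That holds for one assumed scenario. Others give a few percent.
- *That the condition causes the harm.* Step 4 shows that removing it without relabelling would print the gain more often.

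The reply does not remove the conflict between 5.7.3 and 6.3.2, nor the departure from the protocol's definition. It also supplies no rule for which row answers the objective.

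**Conclusion.** The point holds as an internal contradiction and a mislabelled comparator. The contradiction and the departure from the protocol are plain from the text and need no assumptions. The identity shows that month 12 minus month 3 cannot separate maintenance after month 6 from gain before it.

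The size is scenario-dependent. The joint result ranges from 1% to 50% across the cases in Step 3, all with n = 39, a two-sided 5% condition, and assumed rises, falls and SDs. Those figures illustrate the risk and are not an error rate of the plan. What is at stake is the wording of a supportive conclusion on a named secondary objective. The primary result is unaffected. The SAP should still be corrected, because the change alters what may be concluded and costs little.

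**What to change.** Make both changes together:

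1. Delete the condition in SAP 5.7.3, so that month 12 minus month 3 is always calculated, in agreement with 6.3.2 and Table 11.1.
2. State in 5.7.3 and 6.3.2 that the sustainability conclusion for HINT-Q, and for HINT-N through 5.7.4, rests only on the month 6 to month 12 change and its confidence interval, as the protocol defines it. Report month 3 to 6 and month 3 to 12 unconditionally as descriptive time course. State in 6.3.2 and in Tables 11.1 and 13 that these rows carry no sustainability conclusion.

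The first change alone would worsen the problem for the reason shown in Step 4. The cost is SAP wording and labels on four table rows, two in each table. The rows can stay where they are, since Table 10 has no place for them. No data collection, sample size or primary analysis changes, and no comparison is lost.
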